### 8.5 SUBJECT DISPOSITION

Disposition will be summarized by treatment arm for all randomized subjects and will include the number and percentage randomized, the number and percentage who received each dose and the number who completed the trial. The number and percentage of subjects who discontinued will be summarized overall and by reason. The number in each analysis population will also be presented.

### 8.6 DEMOGRAPHIC AND OTHER BASELINE CHARACTERISTICS

Demographic and baseline data will be summarized with descriptive statistics: mean standard deviation, minimum, median, and maximum values for continuous variables, and percentages for categorical variables, by treatment arm, for the mITT population. Prior and concomitant medications will also be summarized with percentages in this fashion.

## 8.7 MEDICAL HISTORY

The percentage of subjects with abnormal medical history findings will be summarized by body system, by treatment arm, for the mITT population.

## 8.8 PRIOR AND CONCOMITANT MEDICATIONS

Prior medications are considered those medications taken prior to the first dose of study drug (i.e., Day 0). Concomitant medications are those used on or after Day 0. Partial start dates of prior and concomitant medications will be assumed to be the earliest possible date consistent with the partial date. Partial stop dates of prior and concomitant medications will be assumed to be the latest possible date consistent with the partial date. Data for all prior and concomitant medications will be summarized with percentages by treatment arm, for the mITT population.

## 8.9 EFFICACY ANALYSIS

The true treatment effect on the primary endpoint is  $p$ , where  $p$  denotes the true population probability of the primary endpoint for each arm. The primary hypothesis of superiority is:

$H_0: p \leq 0.02$  vs.  $H_1: p > 0.02$ , for each treatment arm separately.

A p-value for these hypothesis tests and corresponding 95% confidence intervals will be computed based on the exact method of Clopper-Pearson. Superiority will be concluded if the one-sided p-value is  $< 0.025$  and the corresponding lower bound of the 95% CI exceeds 0.02.

The secondary efficacy binary endpoints will be analyzed in the same manner as the primary hypothesis, but without the hypothesis test p-values.

For the analyses, the efficacy time frame is defined by any time starting from 14 days prior to the -specified visit week.

The anatomic extent endpoint will be analyzed by calculating the mean percent change and associated 95% t-distribution based confidence interval. The percentage of subjects with no clinically significant lesion resolution (reduction in lesion size of 25% or less), partial lesion resolution (26-99% reduction), and complete reduction (100% reduction) will be summarized with point estimates and associated exact Clopper-Pearson 95% confidence intervals.

An exploratory analysis will examine clearance outside of the vulva. This will be analyzed in the same manner as vulvar clearance.

An exploratory analysis will examine the relationship between the primary efficacy endpoint and a) HLA results, b) miRNA results, c) vulvoscopy results, and d) HPV results. Relationships will be examined with contingency tables and/or logistic regression models which model the primary endpoint versus these results and treatment group as regressor variables.

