## 8. STATISTICAL ANALYSIS PLAN

### 8.1 GENERAL CONSIDERATIONS

The statistical analysis of the data will be performed by Inovio Pharmaceuticals or its representative.

This is a two-arm, multi-center, open-label randomized clinical trial of VGX-3100 and VGX-3100 with imiquimod, in subjects with a histologic diagnosis vulvar HSIL and confirmed vulvar infection with HPV types 16 and/or 18. The study's primary endpoint is binary: regression of vulvar HSIL and viral clearance of HPV-16 and/or HPV-18 from vulvar tissue based on tissue collected at Week 48. The primary hypothesis is that each of the treatment arms will result in regression of HSIL and clearance. Secondary efficacy analyses pertain to regression, clearance of HPV-16 and/or HPV-18 infection, regression to normal, non-progression, and anatomic extent. Other secondary analyses concern safety and humoral and cellular immunological measures. Exploratory efficacy analyses concern extended dosing with respect to regression, clearance, and anatomic extent, clearance outside of the vulva, and effect of HLA type on efficacy. Other exploratory analyses pertain to tissue immunological measures and patient-reported outcomes.

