## 8.10 IMMUNOGENICITY ANALYSIS

Post-baseline cellular and humoral response magnitude will be summarized with medians and associated non-parametric 95% CIs. Post-baseline tissue response magnitude will be summarized with means and associated t-distribution based 95% CIs.

Valid samples for statistical analysis purposes will be those collected within 7 or 14 days of the specified time points (see [Table 1](#)). Baseline is defined as the last measurement prior to the first treatment administration.

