All eligible subjects who consent to participate in the study will receive four to six doses of 6 mg of VGX-3100 administered by IM injection followed by EP. The first dose will be administered as soon as possible following confirmation of the HSIL diagnosis, HPV-16/18 status and all other eligibility criteria, but no more than 10 weeks following collection of the subject's biopsy specimen used for diagnosis by the PAC.

Each dose of VGX-3100 will be administered in a 1 mL volume IM followed immediately by EP with the CELLECTRA™ 2000 device. As shown in [Figure 1](#), study subjects will receive at least 4 doses of VGX-3100 and potentially a 5th and 6th dose depending upon their disposition with regard to histologic and lesion area changes. The first dose will be administered on Day 0, the second at Week 4, the third at Week 12, and the fourth dose will be administered at Week 24. Subjects with no HSIL at Week 48 (Subgroups A and B) will receive 4 doses. Subjects with HSIL at Week 48, who have a reduction in lesion size or no increase in lesion size from baseline (Subgroups C or D), may receive a fifth dose of VGX-3100 administered IM with EP at Week 52 per the judgment of the Investigator. Subjects with HSIL at Week 74, who have a reduction in lesion size or no increase in lesion size from baseline (Subgroups C or D), may receive a sixth dose of VGX-3100 administered IM with EP at Week 78 per the judgment of the Investigator. Subjects in Subgroup E may receive surgical treatment per the judgment of the Investigator. All subjects are scheduled to be followed to Week 100.

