### 2.1 PRIMARY OBJECTIVE AND ENDPOINT

Objective	Endpoint
Determine the efficacy of four doses of VGX-3100, alone or in combination with imiquimod, with respect to combined histopathologic regression of vulvar HSIL and virologic clearance of HPV-16/18 in vulvar tissue	Proportion of subjects with no histologic evidence of vulvar HSIL and no evidence of HPV-16/18 at Week 48 in vulvar tissue samples (i.e. collected via biopsy or excisional treatment).

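### Section 8.9 opens the efficacy window 14 days before the visit week and never closes it, so later tissue can enter the Week 48, four-dose primary analysis

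*Protocol*

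**What the plan says.** Protocol Section 8.9 gives one timing rule for all efficacy analyses: "the efficacy time frame is defined by any time starting from 14 days prior to the -specified visit week". It names no closing day and does not say which result counts when a woman has more than one.

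Other parts of the protocol fix the time point and the treatment:

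- Section 2.1, objective: "Determine the efficacy of four doses of VGX-3100, alone or in combination with imiquimod, with respect to combined histopathologic regression".
- Section 2.1, endpoint: "no evidence of HPV-16/18 at Week 48 in vulvar tissue samples".
- Section 8.1 describes the primary endpoint as "based on tissue collected at Week 48".
- Section 2.3, exploratory endpoint 2, assigns Week 74 histology to women who had five doses and Week 96 histology to women who had six.
- Synopsis, Study Design: a woman with HSIL at Week 48 whose lesion has not grown "may receive a fifth dose of VGX-3100 administered IM with EP at Week 52 per the judgment of the Investigator". On the same conditions at Week 74 she "may receive a sixth dose of VGX-3100 administered IM with EP at Week 78 per the judgment of the Investigator".
- Section 8.10 closes its own window: "Valid samples for statistical analysis purposes will be those collected within 7 or 14 days of the specified time points".

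The sentence stands unchanged in every copy of Section 8.9 in the document, the latest being Version 2.0. Section 8.9 of Version 2.1 is not shown, but that version's summary of changes lists no change to it.

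**The concern.** A start with no end makes the Week 48, 74 and 96 windows nested. The Week 48 window then admits tissue taken half a year or more after the visit, some of it after extra doses. This is not detail left to a later document. The protocol states a rule, and the rule permits what the endpoint excludes.

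The primary test compares each arm with a fixed 2% and has no concurrent control, so a change in who is counted, or when, is not balanced by a comparator. The trial is also open-label. If the rule is settled after results are known, the choice between readings is no longer neutral.

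**Working it through.** **Inputs.** Section 8.3: 36 women randomized 2:1 (24 and 12), true rates 20% and 28%, historical rate 2%, one-sided 0.025 per arm, 90% evaluable. Section 8.9: exact Clopper-Pearson test. Table 1: visit weeks and windows. Assumed, because the documents do not give them: how several looks at one woman depend on each other, and how several specimens are resolved.

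**1. The plan's own figure.** Let r be the smallest count with P(X ≥ r | n, 0.02) < 0.025; power is P(X ≥ r | n, p1).

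- VGX-3100 alone: n = 21, r = 3, power 0.821 (n = 20 gives 0.794).
- With imiquimod: n = 10, r = 2, power 0.817 (n = 9 gives 0.766).
- Allowing for 90% evaluable: 21/0.9 = 23.3, so 24; 10/0.9 = 11.1, so 12; total 36.

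The sample size reproduces. The expected evaluable counts are 24 × 0.9 = 21.6 and 12 × 0.9 = 10.8, taken below as 22 and 11.

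**2. The windows in days.**

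- Week 48 is Day 336. Section 8.9 opens at 336 − 14 = 322; the Table 1 visit window is Days 329 to 343.
- Week 74 is Day 518 and opens at 504.
- Week 96 is Day 672 and opens at 658; the visit may run to Day 686.

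With no closing day, the period from 322 contains the period from 504, which contains the period from 658.

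**3. How few women decide an arm.** Clopper-Pearson lower bounds: 3/22 gives 0.029 and 2/22 gives 0.011; 2/11 gives 0.023 and 1/11 gives 0.002. The thresholds are therefore 3 and 2 responders.

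**4. Type I error per arm**, from P(X ≥ 3 | 22, p) and P(X ≥ 2 | 11, p):

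| Reading of the window | p per woman | VGX-3100 alone | With imiquimod |
|---|---|---|---|
| Week 48 result governs, or later looks fully dependent on it | 0.02 | 0.9% | 2.0% |
| Any clean read counts, two independent 2% looks | 1 − 0.98² = 0.0396 | 5.5% | 6.8% |
| Any clean read counts, three independent 2% looks | 1 − 0.98³ = 0.0588 | 13.6% | 13.4% |
| All tissue in the window must be clean | at most 0.02 | at most 0.9% | at most 2.0% |

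With 21 and 10 evaluable, the third row becomes 12.3% and 11.4%.

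**5. Women with no Week 48 tissue.** The plan expects 24 × 0.1 = 2.4 and 12 × 0.1 = 1.2 of them. Section 8.4 admits to mITT any dosed woman who has the endpoint, and Section 8.11.6 imputes nothing, so under Section 8.9 a later biopsy can bring her in. If all of them enter and each carries the 2% background, n becomes 24 and 12 with thresholds still 3 and 2, and type I error is 1.2% and 2.3%. At a 2% background this route changes what is estimated without breaking the 2.5% level. It does harm if response by the later visit exceeds 2%.

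**6. Late conversion, best or latest result counted (illustration).** If the true four-dose rate is 2% and a share c of Week 48 non-responders convert later, p = 0.02 + 0.98c. With c = 5%, p = 0.069 and the chance of declaring superiority is 19% and 17%. With c = 10%, p = 0.118 and it is 49% and 38%. The documents give no value for c.

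**The case against.** The endpoint wording names Week 48 repeatedly, and later tissue has its own exploratory endpoints. One loose general sentence need not displace them, and nothing in the protocol says that Week 74 or 96 tissue will be counted at Week 48.

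A reader might infer that women given doses 5 and 6 will be credited as Week 48 responders and that the type I error is therefore inflated. The documents do not support that. Dose 5 is offered only to women with HSIL at Week 48, so each already has a result in the window that Table 3 classes as non-response. She becomes a responder only if a best or latest result overrides it, and Section 8.9 does not say so. A woman with no Week 48 tissue does not meet the dose 5 condition, so for her a clean Week 74 biopsy is a timing problem, not a fifth-dose effect.

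Direction is also open: requiring all tissue in the window to be clean would lower the count. The independent-looks figures further assume a biopsy of every woman at every visit, whereas women treated surgically or with worsening disease have no further biopsy. The 2% is a historical proportion, not a rate per biopsy. Women given non-study treatment for vulvar HSIL are non-responders under Table 3, so the open window does not credit them.

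All of this stands, and it limits the size of the effect. It does not give the window an end or supply a rule for several specimens. A visit window of ±7 days beside a wider analysis window is not in itself a contradiction; the missing end is.

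**Conclusion.** Wrong as written. Section 8.9 states an open-ended window that conflicts with the Week 48, four-dose primary endpoint and with the exploratory endpoints for five and six doses.

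The surer consequence is that a woman without Week 48 tissue can enter the primary mITT analysis through a later biopsy. The conditional one is that, if any time is taken to mean best or latest result, a woman with HSIL at Week 48 can be counted as a responder after dose 5 or 6. With thresholds of 3 of 22 and 2 of 11, one or two such women can decide an arm.

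Per-arm type I error runs from unchanged (0.9% and 2.0%) to 13.6% and 13.4%, and could fall below the lower figures if all tissue must be clean. The upper end rests on three independent 2% looks with any clean read counting, and covers background regression only. The protocol thus fixes neither the size nor the direction of the effect. The sample size and stated power are not affected.

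**What to change.** Replace the sentence in Section 8.9 with closed, non-overlapping analysis windows:

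- For Week 48, use the specimen nearest Day 336, taken from 14 days before that day up to a stated end that is no later than the Week 52 visit window and before any fifth dose.
- State that the Week 48 result governs the Week 48 endpoints, and that Week 74 and Week 96 tissue serves only the endpoints for those visits. Define those windows in the same way.
- Treat a woman without tissue in the window as having no Week 48 specimen.
- Restate that a woman who received non-study treatment for vulvar HSIL before the Week 48 evaluation stays in the analysis as a non-responder (Table 3). Without this, closing the window could let treated failures drop out of mITT as missing, which would raise the response rate.

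The cost is one paragraph, settled before results are seen. The downside is that a few late biopsies no longer count at Week 48.

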### 3.2.1 DEFINITION OF RESPONDER AND NON-RESPONDER

A treatment responder is defined as a subject with no histologic evidence of vulvar HSIL and no evidence of HPV-16 or HPV-18 in vulvar tissue at evaluation and who did not receive any non-study related treatment for vulvar HSIL. A treatment non-responder is a subject with histologic evidence of vulvar HSIL or vulvar carcinoma at evaluation, or a subject with evidence of HPV-16/18 at evaluation, or a subject who received non-study related treatment for vulvar HSIL. Any case of histologically confirmed progression is considered a non-responder. Progression is defined as advancement to carcinoma by histology according to the PAC.

Responder and non-responder definitions (Table 3) take into account both histopathologic regression of vulvar HSIL and virologic (HPV-16/18) clearance from tissue samples since HPV persistence is an important factor in the clinical progression of HSIL.

Table 3: Definition of Responder and Non-responder	
Responder	Non-Responder
Subject with no histologic evidence of vulvar HSIL AND Subject with no evidence of HPV-16 or HPV-18 in vulvar tissue at evaluation AND Subject who did not receive any non-study related treatment for vulvar HSIL	Subject with histologic evidence of vulvar HSIL or vulvar carcinoma at evaluation OR Subject with evidence of HPV-16 or HPV-18 in vulvar tissue at evaluation OR Subject who received non-study related treatment for vulvar HSIL

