4. Determine the efficacy of four doses of VGX-3100 , alone or in combination with imiquimod, as measured by histologic regression of vulvar HSIL to normal tissue	4. Proportion of subjects with no evidence of vulvar HSIL, no evidence of LSIL (VIN1), and no evidence of condyloma on histology (i.e. biopsies or excisional treatment) at the Week 48 visit
5. Determine the efficacy of four doses of VGX-3100 , alone or in combination with imiquimod, as measured by non-progression of vulvar HSIL to vulvar cancer as determined by histology	5. Proportion of subjects with no progression  of vulvar HSIL to vulvar cancer from baseline to Week 48 visit
6. Determine the efficacy of VGX-3100, alone or in combination with imiquimod, as measured by reduction in the surface area of qualifying vulvar lesion(s)	6. Percent reduction in the cumulative surface area of the acetowhite vulvar lesion(s) as determined by the quantitative analysis of standardized pre-biopsy photographic imaging of qualifying  lesion(s) at Week 48, 74 and 96 compared to baseline  . Results will be classified as: no clinically significant lesion resolution (reduction in lesion area of 0-25%), partial lesion area resolution (>25% and <100% reduction) and complete lesion resolution (no visible lesion).

 No evidence of vulvar HSIL is defined as normal tissue or vulvar LSIL (VIN 1) or condyloma

 Clearance of HPV-16 or HPV-18 is defined as being undetectable by PCR assay.

 Progression is defined as advancement to carcinoma by histology according to the Pathology Adjudication Committee.

 A qualifying lesion is defined as a vulvar lesion which is confirmed to be HPV-16 and/or HPV-18 positive and have histologically confirmed vulvar HSIL by the PAC at screening.

 Baseline photographic imaging is defined as photographs obtained at Day 0 prior to the first study dose. Digital photos will be analyzed with a computer program to calculate the total lesion size in cm^2.

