If after evaluation of the biopsy tissue HSIL remains, but there is a reduction in the qualifying lesion(s) size or no change in lesion size from baseline (Subgroups C or D), the Investigator has the option to give the subject a 5th dose of VGX-3100 at Week 52, and the subject will continue on study with vulvoscopy and biopsy at Week 74. Alternatively, the Investigator may choose to treat the subject with surgical or standard treatment, and the subject will continue on study without further biopsy. A qualifying lesion is defined as a vulvar lesion which is confirmed to be HPV-16 and/or HPV-18 positive and have histologically confirmed vulvar HSIL by the PAC at screening.

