**Figure 4: Evaluation process at Week 100**

In the event of worsening disease at any time (i.e., Subgroup E – any increase in lesion area from baseline or worsening to cancer), the subject will receive surgical treatment per the Investigator's judgment and will continue on study through Week 100 with vulvoscopy, but without further study treatment or biopsy. If at any time in the study carcinoma is discovered, subjects will receive surgical treatment, and be discontinued from study treatment. The event will be reported as an SAE per section 7.1.4. If wide excision is required, the sample obtained will be sent to the PAC for evaluation.

Definition of Responder and Non-responder: Responder and non-responder definitions (Table 3) take into account both histopathologic regression of vulvar HSIL and virologic (HPV-16/18) clearance from tissue samples since HPV persistence is an important factor in the clinical progression of HSIL. A treatment responder is defined as a subject with no histologic evidence of vulvar HSIL and no evidence of HPV-16 or HPV-18 in vulvar tissue at evaluation and who did not receive any non-study related treatment for vulvar HSIL. A treatment non-responder is a subject with histologic evidence of vulvar HSIL or vulvar carcinoma at evaluation, or a subject with evidence of HPV-16/18 at evaluation, or a subject who received non-study related treatment for vulvar HSIL. Any case of histologically confirmed progression from HSIL to carcinoma is considered a non-responder.

Safety Assessment: Subjects will be monitored for:

- 1) Local and systemic events for 7 days following each VGX-3100 dose as noted in the Participant Diary
- 2) All adverse events including SAEs, SUSARs, UADEs, and other unexpected AEs for the duration of the study.

All subjects will be followed for 100 weeks.

Data Safety & Monitoring Board (DSMB): The DSMB will meet quarterly to review safety data and tissue regression and viral clearance results. The DSMB will be charged with advising the Sponsor if there appears to be a safety issue. No formal interim analysis is planned. The following stopping rules will be applied:

- If at any time during the study one-third (1/3) or more of the subjects experience an Adverse Event of Special Interest (AESI), further enrollment and study treatment will be halted immediately until a thorough investigation has been conducted by the Medical Monitor, Principal Investigator (PI) for the trial, and the DSMB.

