- c Screening 12-lead ECG, complete blood count (CBC), serum electrolytes, blood urea nitrogen (BUN), creatinine (Cr), glucose, ALT, CPK and urinalysis performed within 45 days prior to first dose administration.
- d Negative spot urine pregnancy test is required at screening and prior to each study treatment, vulvoscopy and biopsy/surgical excision.
- e At least 34 mL (4 x 8.5 mL yellow (ACD) tubes) whole blood and 4 mL serum per time point. At least 68 mL whole blood and 8 mL serum should be collected prior to first dose. One additional 8.5 mL yellow (ACD) tube to be collected at Day 0, Week 15 and 48 for microRNA analysis.
- f At least 51 mL [6 x 8.5 mL yellow (ACD) tubes] whole blood and 4 mL serum should be collected at Week 27.
- g HLA testing will be performed once from an existing PBMC sample.
- h HPV genotyping and Pap smears are performed on the same ThinPrep® cervical specimen.
- i An additional visit may be scheduled to perform vulvoscopy if worsening of disease is suspected. Biopsies should not be performed at any visit other than at entry (Screening), Week 48, and Weeks 74 and 96 for Subgroups C and D unless the Investigator suspects invasive cancer. All biopsy samples and/or excision samples must be sent to the PAC for review.
- j Photography of the acetowhite stained qualifying lesion(s) must be performed prior to and after biopsy, and at all vulvoscopy examinations. If a pre-biopsy digital photograph is not available for a historical biopsy sample at screening, a post biopsy photo will be sufficient. Additionally, standardized high resolution digital photographic imaging should be obtained during examinations of the vagina if lesions are identified, for documentation.
- k Tissue specimen from all excised tissue must be reviewed by the PAC and residual vulvar tissue from entry, Week 48, 74 or Week 96 specimen(s) (paraffin blocks or unstained slides) must be sent to the central pathology laboratory for HPV testing.
- l HPV genotyping is performed on vulvar tissue specimen using a PCR based assay.
- m Potential dosing at Week 52 and Week 78 is applicable for partial responders only.
- n Subjects will take home imiquimod plus an imiquimod dosing log to document their use of imiquimod. Administration of imiquimod begins on Day 0.

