## 2.2 SECONDARY OBJECTIVES AND ASSOCIATED ENDPOINTS

Secondary Objectives	Associated Secondary Endpoints
1. Evaluate the safety and tolerability of VGX-3100 delivered IM followed by EP with CELLECTRA™ 2000, alone or in combination with imiquimod	1a. Local and systemic events for 7 days following each dose as noted in the Participant Diary. 1b. All adverse events including SAEs, SUSARs, UADEs, and other unexpected AEs for the duration of the study (through Week 100 visit)
2. Determine the efficacy of four doses of VGX-3100, alone or in combination with imiquimod, as measured by histologic regression of vulvar HSIL	2. Proportion of subjects with no evidence of vulvar HSIL on histology (i.e. biopsies or excisional treatment) at Week 48 visit
3. Determine the efficacy of four doses of VGX-3100, alone or in combination with imiquimod, as measured by virologic clearance of HPV-16/18 in vulvar tissue	3. Proportion of subjects with no evidence of HPV-16/18 in vulvar tissue samples at Week 48 visit
4. Determine the efficacy of VGX-3100 , alone or in combination with imiquimod, as measured by histologic regression of vulvar HSIL to normal tissue	4. Proportion of subjects with no evidence of vulvar HSIL, no evidence of vulvar LSIL (VIN1), and no evidence of condyloma on histology (i.e. biopsies or excisional treatment) at the Week 48 visit
5. Determine the efficacy of four doses of VGX-3100 , alone or in combination with imiquimod, as measured by non-progression of vulvar HSIL to vulvar cancer as determined by histology	5. Proportion of subjects with no progression of vulvar HSIL to vulvar cancer from baseline to Week 48 visit
6. Determine the efficacy of VGX-3100, alone or in combination with imiquimod, as measured by reduction in the surface area of the qualifying vulvar lesion(s)	6. Percent reduction in the cumulative surface area of the acetowhite vulvar lesion(s) as determined by the quantitative analysis of standardized pre-biopsy photographic imaging of the qualifying  lesion (s) at Week 48, 74 and 96 compared to baseline  . Results will be classified as: no clinically significant lesion resolution (reduction in lesion size of 0-25%), partial lesion area resolution (>25% and <100% reduction), and complete lesion resolution (no visible lesion).

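### Lesion area at Weeks 74 and 96 has no rule for subjects already treated outside the study regimen for vulvar HSIL, and either reading of the text tends to favour VGX-3100

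*Protocol*

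**What the plan says.** **Endpoint.** Secondary endpoint 6 (Synopsis and section 2.2) is "Percent reduction in the cumulative surface area of the acetowhite vulvar lesion(s) as determined by the quantitative analysis of standardized pre-biopsy photographic imaging", restricted to qualifying lesions, at Weeks 48, 74 and 96 against Day 0. The paired objective presents it as efficacy of VGX-3100. Complete resolution means only that no lesion is visible. Exploratory endpoint 1 (section 2.3) repeats the measure at Weeks 74 and/or 96 in subjects without complete resolution at Week 48.

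**Follow-up after surgery.** If HSIL persists after Week 48 without lesion growth (Subgroups C and D), "the Investigator may choose to treat the subject with surgical or standard treatment, and the subject will continue on study without further biopsy" (Synopsis, Efficacy Assessment). The same option follows Week 74. For worsening disease (Subgroup E) the subject has surgery per investigator judgment and "will continue on study through Week 100 with vulvoscopy, but without further study treatment or biopsy". Table 1 schedules vulvoscopy and photography at Weeks 74 and 96, and its footnote j states: "Photography of the acetowhite stained qualifying lesion(s) must be performed prior to and after biopsy, and at all vulvoscopy examinations".

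**Analysis.** Section 8.9 sets the method: "The anatomic extent endpoint will be analyzed by calculating the mean percent change and associated 95% t-distribution based confidence interval". It also tabulates classes. Section 8.4 takes every treated subject who has the endpoint, and section 8.11.6 uses values as reported, without imputation.

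**Rules that exist elsewhere.** Table 3 (section 3.2.1) makes a "subject who received non-study related treatment for vulvar HSIL" a non-responder. Exploratory endpoint 5 counts only clearance achieved without surgery.

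**Classes.** Section 2.2 begins with "no clinically significant lesion resolution (reduction in lesion size of 0-25"%, then above 25% and below 100%, then no visible lesion. Section 8.9 uses 25% or less, 26-99%, and 100%.

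**The concern.** Lesion area is the outcome that excision changes most directly, yet it is the one for which the protocol writes no treatment rule. Under the decision process, surgery goes to subjects whose HSIL persisted or whose disease worsened. A treatment failure can therefore appear at Week 74 or 96 as a best outcome, or disappear from the denominator. The problem is sharpest in exploratory endpoint 1, whose population is restricted to subjects unresolved at Week 48, the group from which most operated subjects would come. At stake is the interpretation of a named secondary efficacy endpoint at two of its three time points. A smaller matter is that the two sets of classes do not agree.

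**Working it through.** The plan gives no figure on this point, so there is none to reproduce. The check follows the text and then sizes the effect.

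**1. What the text does with an operated subject**
- *She stays on study.* For Subgroups C and D only further biopsy is dropped. For Subgroup E continued vulvoscopy is explicit; for C and D it follows from remaining on study under Table 1.
- *She is photographed.* Footnote j ties photography to every vulvoscopy, not only to biopsy visits.
- *Reading A: her image counts.* She has the endpoint, belongs to the mITT set, and is analysed as measured. If no lesion is visible, that is 100% reduction and complete resolution.
- *Reading B: only pre-biopsy images count.* She has no further biopsy, so she lacks the endpoint, leaves the mITT set, and is not imputed.

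**2. Inputs**
- Arm sizes 24 and 12 (section 3).
- 90% evaluable (section 8.3). This is stated for Week 48; carrying it to Weeks 74 and 96 is an assumption. 24 × 0.9 = 21.6, taken as 22; 12 × 0.9 = 10.8, taken as 11.
- The number operated on, s, is not given.

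**3. Effect per operated subject (reading A, true reduction 0%, measured 100%)**

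Shift in mean reduction and in the complete-resolution rate = 100/n points: 100/22 = 4.5 and 100/11 = 9.1.

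**4. Illustration**

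Assumptions not in the documents: 4 of 22 and 3 of 11 truly resolved; s = 3 in each arm, with no true reduction; all others reduced by 25%. Clopper-Pearson 95% intervals are in brackets.

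| Handling of the 3 operated subjects | Complete resolution, n=22 | Mean reduction, n=22 | Complete resolution, n=11 | Mean reduction, n=11 |
|---|---|---|---|---|
| Kept, pre-surgery area | 4/22 = 18.2% (5.2-40.3) | 775/22 = 35.2% | 3/11 = 27.3% (6.0-61.0) | 425/11 = 38.6% |
| Reading A, as measured | 7/22 = 31.8% (13.9-54.9) | 1075/22 = 48.9% | 6/11 = 54.5% (23.4-83.3) | 725/11 = 65.9% |
| Reading B, dropped | 4/19 = 21.1% | 775/19 = 40.8% | 3/8 = 37.5% | 425/8 = 53.1% |

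The sums are 4×100 + 15×25 = 775 and 3×100 + 5×25 = 425; reading A adds 3×100 to each. Across s = 2 to 6, reading A gives 27.3% to 45.5% complete resolution at n=22 and 45.5% to 81.8% at n=11. With no true resolution at all, three operated subjects alone show 13.6% (2.9-34.9) and 27.3% (6.0-61.0).

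**5. Exploratory endpoint 1**

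If those 4 and 3 had resolved by Week 48, 18 and 8 subjects remain. Three operated subjects then give 3/18 = 16.7% and 3/8 = 37.5% apparent complete resolution under reading A, where the true figure is zero.

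**6. Classes**

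Under section 2.2 a lesion that grows has no class; under section 8.9 it falls in the lowest. Section 8.9 leaves 25-26% and 99-100% unassigned unless percentages are rounded to whole numbers, which it does not say.

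**The case against.** A reader might infer that the plan necessarily analyses surgery as VGX-3100 effect and scores every operated subject as 100% reduced. The documents do not support that. The endpoint specifies pre-biopsy imaging, wording added by amendment, and operated subjects have no further biopsy, so reading B is open. Continued vulvoscopy is spelled out only for Subgroup E. An excised lesion may also recur: section 1.1.4 cites recurrence of up to 45% at three years. This limits the claim to two possible readings, but reading B removes subjects selected for treatment failure, so a rule is still needed.

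A reader might also size the problem by treating the 80% and 72% who are not responders under section 8.3 as candidates for surgery. That base is wrong. Those figures are failure of the composite of histology and HPV clearance, while the surgery option after biopsy requires persisting HSIL. Subjects without HSIL who remain HPV-positive simply continue. No surgery rate can be taken from the documents.

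A separate SAP may contain a rule. That would settle it, but the protocol itself fixes the endpoint, the analysis set and the use of reported values, and writes a treatment rule for other endpoints and not for this one.

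The Section 8 text shown is that of version 2.0. The version 2.1 change list names sections 8.3 and 8.8 but not 8.9, so the wording probably stands; version 2.1's own Section 8 is not in the part available.

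**Conclusion.** The concern holds as a gap with two readings. Following the text either counts excision as lesion reduction or drops the operated subjects. The first favours the drug whenever surgery leaves no visible lesion. The second raises the complete-resolution rate, and raises the mean to the extent that operated lesions had shrunk less than average.

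The size is unknown. The 4.5 and 9.1 points per operated subject rest on 22 and 11 subjects with data, no true reduction, and no lesion visible afterwards.

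Severity is should-fix. The primary endpoint is protected by the non-responder rule. The results mainly affected are Week 74 and 96 summaries without hypothesis tests. Week 48 is largely safe, because an excision at that visit comes after the pre-biopsy image; only earlier surgery for worsening could reach it. The mismatch of classes is real but editorial.

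**What to change.** Amend sections 2.2, 2.3 and 8.9 (and the matching Synopsis entries) to state that, for any area assessment after non-study treatment of vulvar HSIL:
- the last area measured before that treatment is used for both the mean percent change and the class, so the two cannot disagree;
- the subject is never counted as complete resolution;
- the subject stays in the denominator;
- the number so handled is reported per arm and visit.

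Say explicitly that the term covers surgical, ablative and medical treatment, including an excision done under the protocol's own options. Add a matching exception to section 8.11.6, since carrying an earlier area forward departs from its no-imputation rule.

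Use one exhaustive set of classes throughout: 25% reduction or less, including any increase; above 25% and below 100%; no visible lesion.

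The change is wording only. It alters no visit, procedure or clinical decision, and section 6.15 already has procedures during the study recorded on the CRF. The cost is less favourable area results at Weeks 74 and 96. As the trial is open-label, the rule should be fixed before those data are analysed.
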